privilege, whenever possible identifiers will be removed from study-related information, patients' computer medical information will only be available through password access.

Identifiable data will be kept in a single encrypted file on the shared (z:) drive behind the UPMC firewall. All other study-related data (such as paper records and data for analysis) will have all identifiers removed.

View: Pitt SF: Risk and Benefits

Risk and Benefits

1. * Enter all reasonably foreseeable risks, discomforts, hazards, or inconveniences to the subjects related to subjects' participation in the research:

	Research Activity	low dose ketamine infusion
	Other Risks	No Value Entered
VICW	Infrequent Risks	feelings of frustration, embarrassment or boredom
View	Common Risks	No Value Entered
	Research Activity	completion of questionnaires
	Other Risks	No Value Entered
VIOW	Infrequent Risks	Breach of confidentiality
View	Common Risks	No Value Entered
	Research Activity	Collection of information from medical records

Common Risks

No Value Entered

Allergic Reaction (rare) Blurred vision(infrequent) Confusion (infrequent) Drowsiness (infrequent) Increased or decreased blood pressure or heart rate (infrequent) Mental or mood changes (infrequent) Nausea and vomiting (infrequent) Dreams, hallucinations and delirium (infrequent) Liver injury (rare)

Other Risks

With respect to the risk of liver injury, there have been reports of reversible, elevated liver enzymes associated with long term, repetitive use of high dose ketamine, although there are currently no reports of liver injury associate with low dose ketamine, which is used in this study. That being said, you are instructed to notice the following signs and symptoms of liver injury, and

View

	report to physicians with the information of previous exposure of ketamine infusion: • Discolored skin and eyes that appear yellowish • Abdominal pain and swelling • Itchy skin that doesn't seem to go away • Dark urine color • Pale stool color • Bloody or tar-colored stool • Chronic fatigue • Nausea • Loss of appetite
--	---

View	Research Activity	cold pressor test
	Common Risks	No Value Entered
	Infrequent Risks	Excessive painful sensation (rare) tissue damage (rare)
	Other Risks	No Value Entered

2. * Describe the steps that will be taken to prevent or to minimize risks: Experimental Interventions:

Participants will receive ketamine infusion at the in-patient units. Should any complications associated with the medication occur, emergency cart is readily available at the units. Acute Interventional Perioperative Pain Service (AIPPS), which is responsible for the participants' postoperative pain management, is 24/7 available to address any associated issues.

All aspects of patients' analgesic care, including the management of low-dose ketamine infusion, will be administered under the consultation of the acute Interventional Perioperative Pain Service, which routinely uses these infusions in the managment of perioperative pain in opioid dependent or difficult to treat patients. This service is on call 24 hours/day. Ketamine infusions will only be administered to inpatients who are on floors where nursing staff has undergone training in the managment and administration of low dose ketamine infusions.

Patients will be instructed to notice the signs and symptoms of liver injury and report to medical staff about previous exposure to ketamine infusion. Patients will also be followed up for mental status change with Brief Psychiatric Rating Scale.

If the subject is particularly sensitive to the cold pressor test, they will be encouraged to move hand from the ice as soon as they feel any pain sensation. There is a four-minute limit on the test to reduce any risk of tissue damage. The participant will be made aware that they can refuse the cold pressor test should they choose.

Investigators who will access the identifiable medical records already have normal clinical access to all necessary records, as granted by the privacy office for job-related needs. Thus, only HIPAA trained research staff will be handling this information and this information will be stored in a locked

database protected by the UPMC firewall. Additionally, all data generated under this protocol will be monitored and maintained by the principal investigator. Any databases that contain identifiable information will be stored on a departmental drive on the UPMC network created for the principal investigator, and all data will be deidentified according to the HIPPA "safe harbor" guidelines prior to statistical analysis.

Pregnancy is being assessed via a medical record review. Since the ketamine infusion will occur for 48 hours while patient is in the hospital, there is little risk of becoming pregnant during study drug treatment period.

The follow up contact will be made by trained physicians.

Financial ris	sks - will the subject or insurer be charged for any research
required pro	ocedures?
○ Yes ⊙	No

- 4. Describe the steps that will be taken to protect subjects' privacy:
 Research intervention will be conducted in a private room with the patient,
 collected information will be limited to that which is necessary for the goals
 of the research study, access to the patient's private information will be
 limited to those involved in the patient's medical care.
- 5. What steps will be taken in the event that a clinically significant, unexpected disease or condition is identified during the conduct of the study:
 - The patient's primary medical team will be immediately notified of the unexpected, clinically significant condition. The patient's clinically significant medical condition will be managed accordingly. If any of the clinically significant medical condition is related to the study, then the patient's participation in the study will be re-evaluated, with the possibility of the patient being withdrawn from the study if this leads to the resolution of the clinically significant medical condition
- 6. Describe the potential benefit that individual subjects may experience from taking part in the research or indicate if there is no direct benefit. Do not include benefits to society or others:
 Patients with chronic pain and opioid dependence may experience better analgesia in the postoperative period. There is no guaranteed direct benefit to participants.
- 7. Do you anticipate any circumstances under which subjects might be withdrawn from the research without their consent?

Ye	s 🖰	No
----	-----	----

- * Describe the circumstances and any procedures for orderly termination: Subject's failure to follow study procedures Severe allergic reaction to study drug
- 8. Describe procedures that will be followed when subjects withdraw from the research, including partial withdrawal from procedures with continued data collection and data already collected:

If a participant withdraws from research, follow up will cease but data previously collected may still be used in analysis.

View: Pitt SF: Placebo Arm

Placebo Arm

- 1. * Is there a commonly used diagnostic/treatment approach that is currently recognized as being effective for the proposed subjects' disease or condition, and that will be withheld from subjects assigned to the placebo arm of this research study:
 - No subjects assigned to the placebo and experimental arms of the research study will continue to undergo a commonly used diagnostic/treatment approach
- 2. Describe the commonly used diagnostic/treatment approaches that will be withheld from subjects assigned to the placebo arm of this research study: No commonly-used treatment approach will be withheld from the subjects assigned to the placebo arm of this research study.
- 3. Is enrollment into this study limited to individuals in whom the commonly used diagnostic/treatment approaches are known to be ineffective or intolerable?
 - Enrollment into this study is limited to individuals who are opioid tolerant and therefore difficult to treat regarding post operative pain management. Subjects in both arms will receive the same standard of care treatment for post-operative pain management.
- 4. Provide a scientific justification for the placebo-control arm of this research study:

The placebo-control arm will allow for the clinicians to remain blinded to the treatment allocation of participants which will greatly improve the value of the pilot. This research is intended to develop an intervention (continuous, low dose ketamine infusion for 48 hours post-op) that can be implemented in the population from which trial participants are drawn (Opioid tolerant patients). Further, this trial does not require participants to forgo treatment they would otherwise receive

- 5. How long will subjects participate in the placebo arm? Justify why this duration is necessary:
 Subjects randomized in the placebo arm will receive the saline placebo in the exact same fashion as the intervention arm--intraoperatively and then for 48 hours post-operatively.
- 6. How frequently will the subject's condition or disease be monitored and compare that to the frequency of monitoring associated with standard care for this disease/condition?
 Participants in both groups will be monitored by the research team while in the hospital for incidence of adverse events, so they will be monitored more frequently than the standard of care.
- 7. What specific endpoints will result in discontinuing a subject's participation due to worsening of the subject's disease or condition? The same stopping criteria for the intervention arm will be applied to the placebo arm, because clinicians will be blinded to treatment allocation.
- 8. What is the risk to subjects who receive no active treatment for their disease or condition while in the placebo arm? Subjects in the placebo arm will still have their post-operative pain managed as per standard of care for this population at Presbyterian Hospital.
- 9. Describe the planned involvement of a 'contact person' who interacts with the subject on a regular basis and who will notify the investigators immediately of any problems related to the subject's disease or condition: The study coordinator ([name]) will be monitoring the subjects on a regular, daily basis and will notify the PI of any problems related to the subject's condition.

Note: The involvement of the contact person must also be addressed in the consent form

View: Pitt SF: Conflict of Interest

Conflict of Interest

1. *	İs	this	an	FDA	Covered	Clinical	Study?
	\odot	Yes	\circ	Nο			

Answer YES if it is:

- A study of a drug or device in humans to be submitted in a marketing application or reclassification petition that the applicant or FDA relies on to establish that the product is effective (including studies that show equivalence to an effective product); or
- A study in which a single investigator makes a significant contribution to the demonstration of safety.

Do NOT include:

○ Yes • No

- phase I tolerance studies or pharmacokinetic studies;
- clinical pharmacology studies (unless they are critical to an efficacy determination);
- large open safety studies conducted at multiple sites;
- treatment protocols; or
- parallel track protocols.

2. * Does this study involve a Non-Significant Risk Device and you anticipate

- 4. * Is this study funded in part or whole by a PHS Agency?

 O Yes No
- 5. * Does any investigator involved in this study (select all that apply):
 - A. Have a financial interest (aggregated value of equity and remuneration during the past or next twelve months) in a publicly-traded entity that either sponsors this research or owns the technology being evaluated or developed that exceeds a 5% ownership interest or a current value of \$10,000?

 B. Receive remuneration (during the past or next twelve months) from a non-publicly traded entity that either sponsors this research or owns the technology being evaluated or developed that exceeds \$10,000?

 C. Have equity in a non-publicly traded entity that either sponsors this research or owns the technology being evaluated or developed?

 D. Have rights as either the author or inventor of intellectual property being evaluated or developed in this research and for which you are receiving royalties,

	milestone fees, or other proceeds that have or will exceed \$10,000 in any 12-month period (include payments through the University of Pittsburgh, the Veterans Administration Pittsburgh Healthcare System, UPMC, and University of Pittsburgh Physicians)?
	E. Have an officer or management position with a company that either sponsors this research or owns the technology being evaluated or developed?
	F. Receive compensation of any amount when the value of the compensation would be affected by the outcome of this research, such as compensation that is explicitly greater for a favorable outcome than for an unfavorable outcome or compensation in the form of an equity interest in the entity that either sponsors this research or owns the technology being evaluated or developed?
V	None of the above options apply and there are no other financial conflicts of interest in the conduct of this research.

6. Provide the name of the investigator(s) and describe the nature of the Significant Financial Interest(s):

View: Pitt SF: Ancillary Reviews

Ancillary Reviews

1.	Ancillary reviews or notifications selected below are required based on previous answers to questions. If a selection is incorrect, return to the appropriate page and adjust the answers to questions on that page:						
	□ Conflict of Interest (COI)						
	□ Clinical and Translational Research Center (CTR						
	✓ Data Security						
	□ Honest Broker						
	~	✓ UPMC Investigational Drug Service					
		Pitt Medical School Review					

	Su	pport (O3IS)	
	□ spc	RCCO Business Manager (required for industry onsored studies)	
		Religious Directives	
	V	Scientific Review	
		Health Record Research Request (R3) (required ing UPMC clinical data and authorization for other MC data sources for research)	
		UPMC Office of Sponsored Programs and search Support (using UPMC facilities and/or UPI tients during the conduct of the study)	ИС
2.		litional ancillary reviews the PI may choose to include as needed fearch:	for the
		Human Stem Cell Oversight (hSCRO)	
		Institutional Biosafety Committee (IBC)(study volves deliberate transfer of recombinant or synth cleic acid molecules)	etic
		Radioactive Drug Research mmittee (RDRC)(study involves the evaluation or procedures that emit ionizing radiation)	use
		View: Pitt SF: Clinica	l Triale

Good Clinical Practice (GCP) Training

* Regardless of funding source, is this study a clinical trial (as defined by the NIH)?
 Yes No

ClinicalTrials.gov Information

Visit the University of Pittsburgh Office for ClinicalTrials.gov website or contact [contact] further information.

- 2. * Was this study registered, or will it be registered, on ClinicalTrials.gov?
 - Yes No
- **3.** * Is the University of Pittsburgh or UPMC the Sponsor Organization for this study record?
 - Yes No
 - * Who will be the Responsible Party for this study record?

Principal Investigator of this IRB application

View: Pitt SF: Supporting Documents

Supporting Documents

1. Attach any additional supporting documents not previously uploaded. Name the documents as you want them to appear in the approval letter:

Document Category Date Modified Document History

There are no items to display

View: Pitt Create

Add Drug Information

1. Select the drug: Ketamine

If you cannot find the drug in the list above, enter its information here:

Generic name:

Brand name:

2. * Purpose of their use:

KETALAR (generic: ketamine) is a rapid-acting general anesthetic producing an anesthetic state characterized by profound analgesia, normal pharyngeal-laryngeal reflexes, normal or slightly enhanced skeletal muscle tone, cardiovascular and respiratory stimulation, and occasionally a transient and minimal respiratory depression. The mechanism of action is primarily due to antagonism of N-methyl-D-aspartate (NMDA receptors) in the central nervous system.

3. * FDA status:

Drug being used "off-label"

4. Attach files related to this drug:

	Document	Category	Date Modified	Document History
View	memo signed.pdf(0.01)	Drug Attachment	2/12/2019	History
View	FDA exempt.pdf(0.01)	Drug Attachment	2/12/2019	History
View	Ketamine package insert.pdf(0.01)	Drug Attachment	2/12/2019	History

5. Attachments may include a copy of the package insert, investigator brochure, product labeling, or verification of any IND number.

View: Pitt Create

Add Storage Information

- 1. * Select a Storage Type:
 UPMC owned desktop, laptop or other device
- 2. Description:

3. * Will identifiable data be stored in this location?
° Yes [®] No
4. * Will sensitive data be stored in this location?
° Yes [€] No
5. Will de-Identified or anonymous data be stored in this location?
↑ Yes No
 6. * Is anti-virus software installed and up to date on all devices and are the operating systems kept up-to-date on all devices? Yes No
7. Provide additional information as needed:
View: Pitt Create
Add Storage Information
1. * Select a Storage Type: Server: UPMC Managed Server
2. Description:
3. * Will identifiable data be stored in this location? • Yes • No
res No
4. * Will sensitive data be stored in this location? • Yes No

View: Pitt Risk

Risk

- 1. * Research Activity:
 Collection of information from medical records
- 2. Common Risks:
- 3. Infrequent Risks:
 Breach of confidentiality
- 4. Other Risks:

View: Pitt Risk

Risk

- 1. * Research Activity: completion of questionnaires
- 2. Common Risks:
- 3. Infrequent Risks: feelings of frustration, embarrassment or boredom
- 4. Other Risks:

View: Pitt Risk

Risk

1. * Research Activity:
low dose ketamine infusion

2. Common Risks:

3. Infrequent Risks:

Allergic Reaction (rare) Blurred vision(infrequent) Confusion (infrequent) Drowsiness (infrequent) Increased or decreased blood pressure or heart rate (infrequent) Mental or mood changes (infrequent) Nausea and vomiting (infrequent) Dreams, hallucinations and delirium (infrequent) Liver injury (rare)

4. Other Risks:

With respect to the risk of liver injury, there have been reports of reversible, elevated liver enzymes associated with long term, repetitive use of high dose ketamine, although there are currently no reports of liver injury associate with low dose ketamine, which is used in this study. That being said, you are instructed to notice the following signs and symptoms of liver injury, and report to physicians with the information of previous exposure of ketamine infusion:

- Discolored skin and eyes that appear yellowish
- Abdominal pain and swelling
- Itchy skin that doesn't seem to go away
- Dark urine color
- Pale stool color
- Bloody or tar-colored stool
- Chronic fatigue
- Nausea
- Loss of appetite

View: Pitt Risk

Risk

- 1. * Research Activity: cold pressor test
- 2. Common Risks:
- 3. Infrequent Risks:

 Excessive painful sensation (rare) tissue damage (rare)
- 4. Other Risks:

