STUDY: Perioperative Ketamine in Opioid-Tolerant Patients Undergoing Lumbar Spine Surgery: A

Randomized, Double-blind, Place-controlled Trial

Principal Investigator: [name], PhD, MBA

IRB: STUDY19020144

NCT: 04220489

Study Protocol – Approved 09/03/2019

Basic Information

1. * Title of study:

Perioperative Ketamine in Opioid-Tolerant Patients Undergoing Lumbar Spine Surgery: A Randomized, double-blind, placebo-controlled trial

2. * Short title:

Perioperative Ketamine in Opioid-Tolerant Patients Undergoing Lumbar Spine Surgery

3. * Brief description:

The goal of this study is to determine whether comprehensive perioperative administration of the NMDA receptor antagonist ketamine can increase postoperative pain tolerance and reduce opiate consumption in chronic back pain patients undergoing spinal laminectomy/fusion when compared to placebo

Design: Prospective, Randomized, Double-Blind, Placebo Controlled trial involving opiate-dependent patients undergoing lumbar spine surgery. Opioid dependence will be defined as greater than 60 mg oral morphine equivalents/day for greater than one week. Intraoperatively, patients will receive a 1 mg/kg dose of intravenous ketamine or saline with 15 minutes after induction of general anesthesia. Thereafter, a continuous infusion of 0.20 mg/kg/hr ketamine with a maximum dose of 20 mg/hr or saline will be run to conclude at 48 hours after the end of the surgery (fascial closure). The primary outcome measure will be hydromorphone PCA usage during the first 72 hours postoperatively. Secondary outcome measures will be VAS pain scores at rest and with movement in PACU, 24 hr, 48 hr, 72 hr, 2 week (post-op visit), 6 week follow-up visit, as well as, McGill Pain Questionnaire, Pain Catastrophizing Scale, and emotional distress surveys assessing depression and anxiety at preop/screening, postop and 6 week follow-up (PROMIS Emotional Distress-Anxiety Short Form, PROMIS Emotional Distress-Depression Short Form), as well as a Neuro-QOL Short Form v1.1 - Satisfaction with Social Roles and Activities.

4.	* Principal investigator:
	[name]

5 .	*	Does	the	investigator	have a	financial	interest	related	to this	researd	:h?
	- 0	Ye	s 💿	No							

6. * Will an external IRB act as the IRB of record for this study?

O Yes No

- 7. * What kind of study is this? Single-site study
- 8. Attach the protocol:
 - Sponsor/Multicenter protocol
 - Investigator-initiated protocol
 - Emergency Use Consent/ Protocol/ FDA Form 3926

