This medical record review to identify eligible candidates is minimal risk and that the rights and welfare of subjects will not be adversely affected The primary surgeon will identify patients who are prescreened via medical record to be eligible for inclusion, ask them if they would be interested in participating, and if so, the enrollment and consent process would be initiated. Participating neurosurgeons include Drs. [name], who will identify eligible patients. Informed consent will be performed by this Neurosurgeon, the PI, or other co-investigator in the study. Enrollment will be performed by the study coordinator and/or trained representative from the Acute Interventional Perioperative Pain Service (AIPPS). Enrollment will include review of eligibility, and detailed explanation of the study.

5. * Describe all compensation/incentives offered to participants and timing of these offers:

Participants will be compensated up to \$100 for travel and parking expenses related to Pre-Op Visit (\$50) and 6-Week Follow-up visit (\$50)

Recruitment materials: (attach all material to be seen or heard by subjects, including advertisements and scripts)

Document Category Date Modified Document History

There are no items to display

View: Pitt SF: Study Design

Study Design

1. Total number of subjects to be enrolled at this site (enter -1 for chart reviews, banking, registries):
20

2. Describe and explain the study design:

This study is being proposed as a pilot study to inform the feasibility and direction of a larger P01 NIH funded trial.

3. Describe the primary and secondary study endpoints:

Primary Outcome measure:

- ¬ Pre- and post-surgical pain rating
- \neg Pre- and post-surgical opioid utilization (in morphine equivalent units in the PACU and post-operative period until discharge, at 14 days, and at 6 weeks follow-up)
- ¬ Pre- and post-surgical opioid analgesic efficacy

Secondary outcome measures:

- ¬ Mcgill Pain Questionnaire-Short Form
- ¬ Pain Catastrophizing Scale
- ¬ PROMIS Emotional Distress-Anxiety Short Form
- ¬ PROMIS Emotional Distress-Depression Short Form
- ¬ Neuro-QoL Short Form v1.1 Satisfaction with Social Roles and Activities
- ¬ Cold Pressor Test

4. Provide a description of the following study timelines:

Duration of an individual subject's active participation:

6 weeks

Duration anticipated to enroll all subjects:

5 months

Estimated date for the investigator to complete this study (complete primary analyses):

10/31/2019

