1. * Provide a detailed description of all research activities (including screening and follow-up procedures) that will be performed for the purpose of this research study. This description of activities should be complete and of sufficient detail to permit an assessment of associated risks. Patients will be recruited from the UPMC Neurosurgery Clinic. The primary surgeon will identify patients who would be eligible for inclusion, ask them if they would be interested in participating, and if so, the enrollment and consent process would be initiated. The participating neurosurgeon is [name], who has agreed to allow us access to his patients. Informed consent will be performed by [name], or the Pl. Enrollment will be performed by the study coordinator and/or trained representative from the Acute Interventional Perioperative Pain Service (AIPPS). Enrollment will include review of eligibility, and detailed explanation of the study.

Screening Visit: Approximately 1 hour

After patients are enrolled into the study at the preoperative neurosurgery clinic, a number of forms will filled out by the subjects: McGill Pain questionaire-Short form (measures pain), pain medication review form, and the Pain Catastrophizing Scale (PCS) (assesses patient's ability to tolerate pain) PROMIS Emotional Distress-Anxiety Short Form (measures anxiety) and PROMIS Emotional Distress-Depression Short Form (measures depression), Brief Psychiatric Rating Scale (assesses psychiatric state of patient) and Neuro-QoL Short Form v1.1 - Satisfaction with Social Roles and Activities (assesses depression/anxiety when it comes to social roles) will also be completed.

Pre-Operative Visit: Approximately 1.5 hrs

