Randomization will occur by a computer based system at a 1:1 ratio. The Investigational Drug Pharmacy will create the randomization log and IDS will randomize the subject independent of the research team. The study drug/placebo will look identical to maintain the blind for all clinicians and research staff involved.

At the day of surgery, subjects will be seen by team members of the Acute Interventional Perioperative Pain Service preoperatively. Pregnancy will be assessed via medical record, as it is standard of care for these patients to take a pregnancy test day of surgery. Since the ketamine infusion will occur for 48 hours while patient is in the hospital, there is little risk of becoming pregnant during study drug treatment period

Enrolled participants will receive a 1 mg/kg dose of intravenous ketamine or saline 15 minutes after induction of general anesthesia. Thereafter, a continuous infusion of 0.20 mg/kg/hr ketamine or saline with a maximum dose of 20 mg/hr will be run to conclude at 48 hours after the end of the surgery (fascial closure).

A standardized general anesthesia protocol will be used by the hands-on provider. All drugs used intraoperatively, including total hydromorphone dose, will be collected from the electronic medical record.

The amount of narcotics and non-narcotic analgesics administered in the operative and postoperative period will be collected from the electronic chart from day of surgery until discharge. VAS pain scores will be collected

from the PACU until discharge from the hospital.

Pain will be monitored every four hours, except during the night when the participant is asleep. We will use a scale from 0-10, 0 being no pain, 5 being moderate pain and 10 being the worst imaginable pain. The participant will also be asked to score pain at its best and worst over the period since they were last asked.

Post-Op Visit: Approximately 1 hour

Patients will follow-up at Neurosurgery clinic at 10-14 days postoperatively. At this time daily opioid usage will be assessed and converted to morphine equivalents/24 hr. At this visit, the McGill Pain questionnaire-Short form, pain medication review form, and the Pain Catastrophizing Scale (PCS) (Sullivan, 1995). PROMIS Emotional Distress-Anxiety Short Form and PROMIS Emotional Distress-Depression Short Form, Brief Psychiatric Rating Scale and Neuro-QoL Short Form v1.1 - Satisfaction with Social Roles and Activities will also be completed by the participant.

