2.

Refer to the following templates and instructional documents:

- Guidance Consent Wording
- Template Consent Document Short Form
- HRP-090 SOP Informed Consent Process for Research
- HRP-091 SOP Written Documentation of Consent

View: Pitt SF: Medical Records

Medical Records

1. You are required to submit this study to the Research Informatics Office, Health Record Research Request (R3). Per UPMC Policy HS-RS0005, all research projects that access or involve UPMC electronic protected health information (e-PHI) must be submitted to R3, with the exception of clinical trials that are contracted through the UPMC Office of Sponsored Programs and Research Support (OSPARS).

Complete the R3 intake form available at http://rio.pitt.edu/services. An R3 representative will conduct a review. You will be notified once your R3 review is complete or if anything further is needed.

* Describe the protected health information that will be collected from the covered entity and/or the research derived information that will be placed into the medical records:

Patient demographics and medical history will be collected from the medical record

The amount of narcotics and non-narcotic analgesics administered in the operative and postoperative period will be collected from the electronic chart from day of surgery until discharge. VAS pain scores will be collected from the PACU until discharge from the hospital.

View: Pitt SF: Electronic Data Management

Electronic Data Management

1. * Will only anonymous data be collected (select NO if identifiers will be recorded at anytime during the conduct of the study)?

° Yes [®] No

Select all identifiers to be collected during any phase of the research including screening:

E-mail address: Social security #: Phone/Fax #: Account #: Medical record #:	Web Unit Social se Full face images: Health pl Device ic	Protocol (IP) Address: versal Resource Locators (URLs): ecurity # (for Vincent payment only): photo images or comparable an beneficiary #: lentifiers/serial numbers: dentifiers/serial #/license plate #: c identifiers, finger and voice	
a: Will you be collect the following locating geographic subdiving than a State such a address, city, countainty geocodes, etc. b: Will you be collected: b: Will you be collected: b: Will you be collected:	on data: isions smaller is street ty, precinct, ? cting any date s birth date, discharge, vice? hique s, codes related	Yes ○ NoYes ○ No	

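### The primary pain rating names no instrument or baseline, and the VAS/0-10 score used in hospital has no scheduled value before surgery

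*Protocol*

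**What the plan says.** Study Design, item 3 of the protocol puts "Pre- and post-surgical pain rating" first among the primary outcomes. It gives no scale, no baseline time and no post-operative time for it. The McGill Short Form appears in the same item as a separate, secondary outcome.

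Study Aims, item 1 states the pain hypothesis in terms of VAS scores. The Brief description (Basic Information, item 3) treats VAS as secondary and schedules it as "VAS pain scores at rest and with movement in PACU, 24 hr, 48 hr, 72 hr, 2 week (post-op visit), 6 week follow-up visit". The Medical Records section says "VAS pain scores will be collected from the PACU until discharge from the hospital", and the Surgical Visit text says the same. The Surgical Visit text also describes four-hourly monitoring: "We will use a scale from 0-10, 0 being no pain, 5 being moderate pain and 10 being the worst imaginable pain".

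On dosing, the Surgical Visit text says "Enrolled participants will receive a 1 mg/kg dose of intravenous ketamine or saline 15 minutes after induction of general anesthesia". Before surgery, the Screening Visit lists "McGill Pain questionaire-Short form (measures pain), pain medication review form", and the Pre-Operative Visit gives the McGill questionnaire twice.

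The SAP names no outcome. It says that analysis will be mainly descriptive and that a two-sample t test may be used.

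**The concern.** An outcome worded as before and after surgery needs a value on each side, on one scale. The natural scale here is the VAS/0-10 score: the hypothesis uses it, and it is the only pain score taken while study drug is running. Followed as written, the plan gives that scale no value before dosing starts.

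Everyone enrolled has had back pain for more than three months, so pain before surgery is an obvious source of variation between patients. In a small trial reported mainly as arm summaries, a reader would want to see where each arm started on the scale on which it finished. The study is also meant to inform a larger trial. The pre-post correlation and the SD of change are figures that such a pilot can supply, and on this scale it could not. A baseline missed before dosing cannot be collected afterwards.

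**Working it through.** There is no planned figure to reproduce: the documents give no power calculation, effect size or SD for this outcome. The main check is to set each contact in Research Activities, item 1 against the start of study drug.

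| Contact | VAS or 0-10 rating stated | McGill stated |
|---|---|---|
| Screening Visit | none | once (Short Form) |
| Pre-Operative Visit | none | twice: after the first cold-pressor test and before the opioid dose; then after the dose and the second cold-pressor test |
| Day of surgery, before induction | none | none |
| *Study drug starts 15 minutes after induction* | | |
| PACU to discharge | yes | none |
| Post-Op Visit, 10-14 days | none in the visit text; the Brief description lists VAS at 2 weeks | once (Short Form) |
| 6-Week Follow-Up Visit | none in the visit text; the Brief description lists VAS at 6 weeks | once (Short Form) |

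Pre-surgical count: VAS or 0-10 = 0; McGill = 1 + 2 = 3. The cold-pressor test yields times in seconds, not a pain rating.

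This leaves two readings of the primary outcome:

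- **VAS/0-10.** The post-surgical side is well covered in hospital. The pre-surgical side has no scheduled value, and the PACU score cannot stand in because the bolus and intraoperative infusion come before it.
- **McGill.** Both sides exist, at 10-14 days and 6 weeks. But the outcome then duplicates a listed secondary, says nothing about the in-hospital period, and has three candidate baselines. Two of these follow ice-water immersion, and one of those two also follows an opioid dose.

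**Size of what is lost on VAS/0-10.** Inputs: 20 patients (Study Design, item 1) and 1:1 allocation (Surgical Visit), so about 10 per arm. The pre-post correlation r is not given; I assume 0.3 to 0.5.

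1. SE of the baseline difference between arms = SD × sqrt(1/10 + 1/10) = 0.447 SD. The 95% range of chance imbalance is ±1.96 × 0.447 = ±0.88 SD.
2. Only the part correlated with the post-operative score carries through: r × 0.88 = 0.3 × 0.88 = 0.26 to 0.5 × 0.88 = 0.44 post-operative SD, at the edge of that range.
3. Baseline adjustment multiplies the SE of the arm difference by about sqrt(1 − r²): sqrt(1 − 0.09) = 0.95 to sqrt(1 − 0.25) = 0.87. That is a reduction of about 5% to 13%, before the small cost of estimating one slope from 20 patients.

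**The case against.** The strongest reply is that the outcome names no instrument, so nothing ties it to VAS. A reader might infer from the VAS schedule that the pre-surgical half of the outcome does not exist, or that it cannot be computed. The documents do not support that. McGill, which the protocol itself describes as measuring pain, is given three times before surgery and again at both follow-up visits. Its secondary listing argues against that reading but does not exclude it. This part of the reply stands.

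A reader might also infer that a chance baseline imbalance would bias the result. It would not. The arms are randomised, no change score or adjustment is planned, and chance imbalance is already part of the standard error of a two-sample comparison. Nor would imbalance be wholly hidden: pre-operative McGill, medication review and Pain Catastrophizing scores would all show differences between arms. This also stands, and it confines the loss to precision, description and planning data.

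Finally, this is a 20-patient, mainly descriptive pilot with two other primary outcomes, one of which (opioid analgesic efficacy) has an explicit pre-operative measurement. That lowers the priority. It does not remove the point, because informing the larger trial is the pilot's stated purpose.

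**Conclusion.** The point holds in a limited form. The primary pain rating has no named instrument or baseline. On VAS/0-10, the scale of the hypothesis and of the in-hospital record, there is no scheduled pre-surgical value. A pre/post comparison is possible on McGill at 10-14 days and 6 weeks only.

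The comparison between arms remains valid. The losses are the pre-to-post change on VAS/0-10, an SE reduction of roughly 5% to 13%, a same-scale check on arms whose baseline means could differ by up to about 0.88 SD by chance, and the pre-post correlation and SD of change for the larger trial.

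The numbers assume 10 patients per arm and a correlation of 0.3 to 0.5, which the documents do not give. The count of zero covers ratings described in the protocol text. The attached questionnaires cannot be seen, so whether any form contains its own rating item is unknown. For a pilot of this kind, the change is worth making before enrolment but is not a condition for running the study.

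**What to change.** In Study Design, item 3, name the 0-10 rating used in hospital as the instrument for this primary outcome, and state the post-operative times at which it is read. Collect the same rating (current, best and worst) at the existing Pre-Operative Visit, before both the cold-pressor test and the opioid dose, and name that score as the baseline. Optionally repeat it when the pain service sees the patient on the day of surgery, before induction. In the SAP, say that post-operative ratings will be reported alongside the baseline and adjusted for it.

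Defining the outcome on McGill with one designated administration as baseline would need no new data. It would, however, leave the in-hospital period without a baseline and duplicate a secondary outcome, so it is the weaker choice.

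While amending, reconcile the 2-week and 6-week VAS in the Brief description with the visit texts, which list none.

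The cost is one short question set at contacts that already exist and a minor amendment, with no added visit. One limit remains: the Pre-Operative Visit score is taken as a home opioid dose falls due, whereas in-hospital scores are taken under post-operative analgesia. It can serve as a covariate, but change from it needs that caveat.
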